## 1. Revision History

Revision		Date	
A		12 October 2018	

### 1.1. List of Abbreviations

AE	Adverse Event
AHI	Apnea Hypopnea Index
APAP	Automatic Positive Airway Pressure
Bi-level PAP	Bi-level Positive Airway Pressure
CIA	Clinical Investigation Administration
CIP	Clinical Investigation Plan
CPAP	Continuous Positive Airway Pressure
CRF	Case Report Form
FPH	Fisher & Paykel Healthcare
GCP	Good Clinical Practice
HA	Hazard Analysis
IB	Investigators Brochure
ICF	Informed Consent Form
ICH	International Conference on Harmonization of Technical Requirements for Registration of Pharmaceuticals for Human Use
OSA	Obstructive Sleep Apnea
PAP	Positive Airway Pressure
PDS	Pulmonary Disease Specialists
SAE	Serious Adverse Event
UI	User Instructions

## 2. Document Information

### 2.1. Purpose and Scope

The purpose of the trial is to evaluate the performance, comfort and ease of use of the F&P full face mask in the home environment.

## **2.4. Monitoring Arrangements**

FPH will be conducting the study, and as such the investigators or their nominees will monitor the progress of the investigation. The Principal Investigator will have access to all source documents needed to verify the entries to the Case Report Form (CRF) and other protocol related documents; provided that participant confidentiality is maintained in agreement with local regulations it will be the principal investigator's responsibility to inspect the CRF at regular intervals throughout the investigation, to verify the adherence to protocol and the completeness, consistency and accuracy of the data being entered on them.

The investigator's file will contain the protocol/amendments, financial agreement, CRFs and data clarification and query forms, independent Review Board (IRB) approval with correspondence, informed consent, staff curriculum vitae and authorization forms, screening and enrolment logs, and other appropriate documents/correspondence as per International Conference on Harmonization (ICH) and Good Clinical Practice (GCP) and local regulations.

## **2.5. Data Management**

Data obtained for this investigation will be stored in the controlled document system and electronically on secure servers, which are only accessible by Clinical Research staff and those persons identified on the delegation of authority. Any data which is not kept in this secure manner will be de-identified in accordance with HIPPA protocols. Data obtained for this investigation will be recorded in source documents and attached to the CRF for both the administration of the study and collection of participant data.

Original CRFs will be stored for 15 years by FPH. Copies of the CRF will be stored on site Pulmonary Disease Specialists (PDS) for 15 years.

## 5. Device Information

### 5.1. Identification of the Medical Device

The F&P Full face toffee mask is a Full face mask primarily used in sleep laboratories and in home use for the treatment of OSA using CPAP device.

### 5.2. Device Risk Analysis and Management

Positive airway pressure (PAP) therapy via a nasal or oro-nasal mask is standard clinical practice for participants with OSA. The risks associated with this treatment are limited to the potential for slight discomfort associated with the use of a oro-nasal mask during sleep.

[REDACTED]

## 6. Justification for a Clinical Trial

### 6.1. Synopsis

The investigation is a prospective, non-randomized, non-blinded, study. The investigation is designed to evaluate the performance, comfort and ease of use of the F&P Toffee Full Face mask amongst OSA participants. Up to 45 OSA participants who currently use a full face CPAP mask will be recruited.

The Institution will recruit all participants within two weeks of the beginning of the study. This study will involve a baseline visit (Visit 1) where the investigator will obtain participants informed consent for the [REDACTED] and the Anthropometric 3D Scanning study [REDACTED]. Participant's demographics and prescribed PAP therapy treatment settings and mask details will be gathered using the participants questionnaire (Appendix B). [REDACTED] device will be issued to the participant during this visit (if required) Visit 2 will take place  $7 \pm 4$  days after Visit 1. At this visit participants will be fitted with the [REDACTED] mask as well as being asked questions in the form of a structured questionnaire. Participants initial impressions, comments and photographs will be captured via recorded audio and video (both with their consent).

Visit 3 will take place 14 ± 4 days after Visit 2. The participants will come in for a final visit to return the trial mask and provide their feedback in the form of verbal comments and a structured questionnaire. Photographs will be captured as well as audio and video recorded during this visit.

The mask and CPAP (if from the research pool) will be returned to the Institution at the conclusion of the trial and the participant will return to their previous mask and mode of device treatment.

This study will be conducted in accordance with ICH/GCP guidelines. No deviation from the protocol will be implanted without prior review and approval of the sponsor except where it may be necessary to eliminate an immediate hazard to a research participant. In such case, the deviation will be reported to the sponsor as soon as possible. In this trial the sponsor and the investigator are the same company however the sponsor will not be the investigator. To ensure roles are clearly defined and kept independent there will be a delegation of authority log to clearly delineate each individuals tasks.

## **6.2. Literature Review**

Obstructive Sleep Apnea (OSA) is a common sleep breathing disorder effecting around 3-7% of men and 2-5% of women in the general population and is characterized by periodic collapse of the upper airway during sleep. The standard treatment for obstructive sleep apnea is nasal continuous positive airway pressure (CPAP), which consists of pressurized air applied to the nose via an interface. Despite the effectiveness of CPAP in abolishing upper airway obstruction, acceptance of and adherence with therapy has been sub-optimal. Reasons for the low adherence include nocturnal awakenings, incorrect therapeutic pressure and primarily discomfort due to mask poor interface fit. Poor interface fit can result in facial abrasion, leak causing fluctuations in therapeutic pressure and irritation of the eyes .

## **6.3. Preclinical Testing**

[REDACTED]

## **6.4. Previous Clinical Experience**

[REDACTED]

## **6.5. Justification for Administration**

Participants will remain on their prescribed PAP pressure throughout the duration of the trial. Participants will not be randomised to use the investigational mask in home for 14 ± 4 days.

Participants are required to use the investigational mask to provide subjective feedback in terms of comfort and acceptance to ensure advances in interfaces can be made.

## 7. Objectives of the Clinical Investigation

### 7.1. Hypothesis

### 7.2. Objectives

Primary objectives:

The purpose of this clinical investigation is to evaluate the performance, comfort and ease of use of the F&P Toffee full face mask in a home environment.

### 7.3. Population

Up to 45 participants will be recruited for the trial. These participants will be current full face mask users.

Participants will consist of male and female adults diagnosed with OSA who are using either APAP, CPAP or Bi-level with the following recruitment goals:

After identification, the co-ordinating investigator or contact persons from the institution (or those identified by delegation log) will contact potential participants and obtain informed consent from those participants to be enrolled.

### 7.4. Risks

## 7.5. Essential Requirements of the Relevant Directive

Essential requirements are not applicable since this study is being conducted in the USA only.

## 8. Clinical Investigation Design

### 8.1. Type of Investigation

This is an open-label (investigators and participants are un-blinded and informed of intended treatment device) single arm study. The F&P Toffee full face mask will provide effective treatment similar to the participant's usual CPAP mask. The intended treatment F&P Toffee full face mask will not be randomized- as the intention is not to compare between therapies.

### 8.2. Controls

No control group will be used in this study, as it is designed to test the performance and satisfaction of the F&P Toffee full face mask and inform product development.

### 8.3. Bias

The F&P mask is non-blinded and distinguishable. Since the trial mask is the same for the entire population, this study is not blinded.

### 8.4. End Points

#### 8.4.1. Primary Endpoints

- The F&P mask is comfortable to use for the participant as measured by the custom questionnaires and recorded during the interviews.
- The F&P mask is easy to use, accepted by the participant and provides adequate treatment for OSA during in-home use, measured via participant feedback and PAP data download.
- The acceptability of the F&P mask through interview feedback/ questionnaires.

#### 8.4.2. Secondary Endpoints

- To obtain 3D face scanning and head measurements to assist with future product development

## 8.5. Variables

Variable	Justification	Measurement
Ease of use/ Acceptability	To assess the ease of using the mask in the home and overall mask acceptability.	
Mask performance	To assess the masks performance in relation to leak	

Mask Comfort	To assess the comfort (or lack of) of the mask as experienced by the participant while using it in-home.
General Demographics	To gather participants general demographics
Preference	To assess which mask the participants prefers to use going forward.
Anthropometric Scans	To assist with future product development

## 8.6. Measurements

## **8.8. Inclusion / Exclusion criteria**

Inclusion Criteria:

- Adult (22+ years of age)
- Able to give informed consent
- AHI  $\geq 5$  on diagnostic night
- Either prescribed APAP, CPAP or Bi-level PAP for OSA
- Fluent in spoken and written English
- Existing Full Face mask user

Exclusion Criteria:

[figure not shown]
- Inability to give informed consent
- Participant intolerant to PAP
- Anatomical or physiological conditions making PAP therapy inappropriate
- Current diagnosis of respiratory disease or CO2 retention
- Pregnant or may think they are pregnant.

## **8.9. Point of Enrolment**

Participants will be recruited; who are prescribed either APAP, CPAP or Bi-level PAP for OSA at Pulmonary Disease Specialists (PDS). The principal investigator (or those identified in the delegation log) will ask the participants whether they are interested to take part in the trial. The participants who meet the inclusion/exclusion criteria and provide informed consent and will then be enrolled in to the trial. A recruitment script will be used when recruiting participants to the trial.

## **8.10. Patient Procedure**

The study coordinator will ask the participants whether they are interested to take part in the trial. Only eligible participants, that provide written informed consent, will be enrolled into the investigation.

## **8.11. Withdrawal Criteria**

Participants will be informed that they have the right to withdraw from the study at any time, without prejudice to their medical care, and are not obliged to state their reasons. The participants is informed that they can revert back to their usual therapy during the clinical investigation if they have reason to do so. Additionally the investigator may withdraw a participant at any time for the following reasons:

- Protocol Violation
- Safety concerns
- Serious illness
- Adverse event

The reason for participant discontinuation in the study is to be recorded in the CRF and source document.

## **8.12. Number of Trial Participants**

Up to 45 full face mask users for OSA therapy will be recruited in to this study.

## **8.13. Follow up Plan**

Participants will receive standard care from their health care provider throughout and following the study.

## **9. Clinical Trial Documentation**

## **STATISTICAL CONSIDERATIONS**

### **9.5. Description of the Statistical Design**

Since the trial is to inform product development, no statistical design is required.

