### **9.6. Sample Size**

From the 'Guidance for Industry and Food and Drug Administration Staff – Applying Human Factors and Usability Engineering to Optimize Medical Device Design' document issued on 3 February 2016, a number of 30 users will be sufficient to find a minimum of 97% of problems and on average can find 99% of all problems. Additionally from previous experiences, a number of 30 users was not quite achieved when taking into account drop outs and no shows hence the recruitment drive for up to 45 participants has been set.

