## **11. Publication Policy**

This study is intended for internal use on the development of the product. However the results of this study may be used for marketing purposes or in regulatory documentation to support the clinical efficacy of the devices.

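### Section 9.5 waives a statistical design because the trial serves product development, but section 11 also lets the results support clinical efficacy, a use that reason does not cover

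*Combined protocol and SAP*

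**What the plan says.** Section 9.5 is a single sentence: "Since the trial is to inform product development, no statistical design is required". Section 11 begins in the same spirit, "This study is intended for internal use on the development of the product", and then adds an exception: "the results of this study may be used for marketing purposes or in regulatory documentation to support the clinical efficacy of the devices".

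On design, section 8.1 describes an open-label, single-arm study without randomisation, "as the intention is not to compare between therapies". Section 8.2 adds "No control group will be used in this study" and describes the study as a test of performance and satisfaction as well as an input to development. One primary endpoint in 8.4.1 is that the mask "provides adequate treatment for OSA during in-home use, measured via participant feedback and PAP data download"; acceptability is another.

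On size, section 9.6 states that "a number of 30 users will be sufficient to find a minimum of 97% of problems" and sets recruitment at up to 45 to allow for drop-outs and no-shows.

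On the analysis set, section 9.10 includes participants who consent, are fitted, and try to sleep in the mask. It refers to 8.10 for participant flow.

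Several relevant parts cannot be read in the public document: the 7.1 hypothesis, the Measurement column of 8.5, section 8.6, most of 8.10, the 9.7 pass/fail criteria (listed in the contents) and Appendix B. Nothing is claimed about what they contain.

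**The concern.** A waiver of statistical design is reasonable when results feed back only to the design team. It is harder to defend when the same results may go to a regulator as evidence of efficacy. The adequate-treatment endpoint means efficacy-type data will exist. If the section 11 option is used, a figure from an uncontrolled group of people already established on a full face mask could be filed as efficacy support. The visible text specifies no estimate, precision or method of analysis for that purpose. An analysis chosen after the data are seen is weaker support than one fixed beforehand.

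A separate, smaller matter concerns acceptability. A person who is fitted, dislikes the mask and declines to sleep in it has given a clear negative answer on a primary endpoint. Section 9.10 leaves that person out of the analysis.

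**Working it through.** **1. Reason for the waiver against permitted use.** The only reason in 9.5 is product development. Section 11 permits three uses: internal development, marketing, and regulatory documentation supporting efficacy. The reason covers the first. It does not reach the third, and section 11 itself introduces the outside uses as an exception to the internal purpose.

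**2. Does the sample size fill the gap?** The plan's figures are 30 users, at least 97% of problems found, and 99% on average. They are attributed to a guidance document, and no per-user detection probability p is given, so they cannot be reproduced from the plan's inputs. As a check, treat the chance that at least one of 30 users meets a given problem as 1 − (1 − p)^30 and solve for p:

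- 97%: p = 1 − 0.03^(1/30) = 0.110
- 99%: p = 1 − 0.01^(1/30) = 0.142

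The allowance from 30 to 45 corresponds to a loss of 1 − 30/45 = 33%, since 30/(1 − 1/3) = 45. No loss rate is stated. These figures concern discovering problems. None concerns estimating an efficacy measure.

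**3. Precision an efficacy figure would have.** Inputs: n = 30 and n = 45 from 9.6, and an assumed observed proportion of 80%, which is not in the documents. The exact (Clopper-Pearson) 95% limits for x successes out of n are the 0.025 quantile of Beta(x, n − x + 1) and the 0.975 quantile of Beta(x + 1, n − x).

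| n | x | Observed | Exact 95% CI | Width (points) |
|---|---|---|---|---|
| 30 | 24 | 80.0% | 61.4% to 92.3% | 92.3 − 61.4 = 30.9 |
| 45 | 36 | 80.0% | 65.4% to 90.4% | 90.4 − 65.4 = 25.0 |

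At an assumed 90% with n = 30 (27/30) the interval is 73.5% to 97.9%, a width of 24.4 points. The argument does not depend on these assumed rates. They show only the order of precision that the visible plan does not discuss.

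**4. Effect of the 9.10 set on acceptability.** Let a participants accept the mask out of m who tried to sleep in it, and let r reject it before trying. The 9.10 set gives a/m. Counting the r people as not accepting gives a/(m + r), which is smaller whenever a and r are above zero. The exclusion therefore can never lower the apparent rate. For example, with an assumed 24/30 = 80.0%, a single pre-sleep rejection gives 24/31 = 77.4%. The documents give no value for r.

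**The case against.** The best defence is that section 11 is permissive and its first sentence keeps the purpose internal. A usability study needs no formal design, and no planned conduct or analysis changes. That stands, and it limits the point to a mismatch between a stated reason and a permitted use. It does not remove the mismatch.

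A second defence is that 9.7, 8.6 or Appendix B may define a measure or criterion. That also stands. It would not extend the reason in 9.5 to the section 11 use, but it rules out saying that no threshold exists.

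A reader might infer several stronger things that the documents do not support:

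- *Section 11 claims efficacy similar to the usual mask.* It makes no comparison. The statement that the mask "will provide effective treatment similar to" the participant's usual one is in 8.1, which then disclaims any intention to compare.
- *The design is about usability alone.* Section 8.2 covers performance and satisfaction, and 8.4.1 includes adequate treatment. Only the size rests on finding usability problems.
- *The analysed number will fall below 30.* Section 9.6 gives the past shortfall as the reason for recruiting up to 45.
- *Section 9.9 contradicts 9.5 by mentioning a statistical plan.* That wording can refer to the Statistical Considerations section itself.

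On 9.10, it can fairly be said that this is a separate issue and that 6.1 provides for initial impressions and a questionnaire at the Visit 2 fitting. The feedback is therefore collected, but the 9.10 rule still keeps these people out of the analysis.

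**Conclusion.** The mismatch between 9.5 and section 11 is real and in current text. The study can describe how the mask performs and is received among existing full face mask users. On the visible text it was not planned to support an efficacy claim. The weight is modest: section 11 allows the use without committing to it, and a reader should not infer that efficacy is a second objective or that such a claim will be made. The interval widths of about 25 to 31 points at an observed 80% are illustrative and rest on that assumed rate.

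The 9.10 point holds separately. Its direction is certain, its size is unknown, and it falls away if the unseen part of 8.10 already handles these participants.

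**What to change.** **Main change, section 11.** Delete the closing words that offer the results as support for clinical efficacy. Limit external use to descriptive findings, stated as coming from an open-label, single-arm study without a control group. This is a one-sentence edit and leaves design, size and 9.5 untouched. The cost is less freedom in promotional and regulatory use.

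**Only if the efficacy use is kept.** Before the first Visit 2, when the trial mask is first fitted, replace the 9.5 waiver with a short estimation plan. It should:

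- report the adequate-treatment measure from the PAP download as a proportion with an exact 95% confidence interval;
- use any measure or 9.7 criterion already defined in text not visible here;
- state the denominator and how participants without a download are counted;
- make no comparative claim.

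This needs no extra participants. The cost is a short document and an openly wide interval.

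**Separately, section 9.10.** Keep the present analysis set, and also report acceptability among all participants in whom fitting was attempted, counting rejection before sleep as not accepted, unless 8.10 already provides for this. The cost is one extra line of results and a possibly less favourable figure.

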### **9.6. Sample Size**

From the 'Guidance for Industry and Food and Drug Administration Staff – Applying Human Factors and Usability Engineering to Optimize Medical Device Design' document issued on 3 February 2016, a number of 30 users will be sufficient to find a minimum of 97% of problems and on average can find 99% of all problems. Additionally from previous experiences, a number of 30 users was not quite achieved when taking into account drop outs and no shows hence the recruitment drive for up to 45 participants has been set.

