### **9.10. Selection Criteria**

All participants who consent, and are fitted with a mask that they attempt to sleep on will be included in the analysis. Please see section 8.10 for information on participant flow throughout the trial.

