## **10.2. Foreseeable Adverse Events**

The participants may experience a poor night's sleep with the F&P Toffee full face mask as it will be different to the participants usual mask.

Participants may experience the following:

- Pressure sores which may resolve in cuts, rashes and skin abrasions and skin breakdown
- Air leaks into the eye which may cause discomfort, dryness and irritation
- Abrasions to the skin from the headgear
- Eyelid injury and scratches while removing the mask
- Allergies to the mask material
- Collapsing or passing out possibly due to lack of oxygen which can lead to suffocation in some circumstances
- Pressure discomfort in, around, on the sides and under the nose as their usual mask seal and frame may be configured differently

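### Section 9.6 presents finding at least 97%, and on average 99%, of problems as a property of 30 users alone, without the problem frequency on which any such figure depends

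*Combined protocol and SAP*

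**What the plan says.** Section 9.6 (Sample Size) attributes two figures to a 2016 FDA guidance on human factors: "a number of 30 users will be sufficient to find a minimum of 97% of problems", and 30 users "on average can find 99% of all problems". It limits neither figure by how common or severe a problem is, or by how reliably it would be noticed. It then sets recruitment at up to 45, because earlier studies fell short of 30 after losses. No loss rate is given.

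Section 9.5 states: "Since the trial is to inform product development, no statistical design is required". In the visible text, 9.6 is therefore the only quantitative statement of what 30 users can show.

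Three other sections bear on how the figure might be used:
- Section 9.10 defines who is analysed: "All participants who consent, and are fitted with a mask that they attempt to sleep on will be included in the analysis".
- Section 10.2 lists foreseeable adverse events, among them "Allergies to the mask material" and "Eyelid injury and scratches while removing the mask".
- Section 11 describes the study as meant for internal development, but adds that "the results of this study may be used for marketing purposes or in regulatory documentation to support the clinical efficacy of the devices".

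**The concern.** The number of users does not by itself fix the share of problems found. A problem that affects one user in three will almost certainly appear among 30 people. One that affects one user in a hundred will usually not. A statement that 30 users find "a minimum of 97% of problems" therefore needs either a frequency or a description of the set of problems to which it applies. Section 9.6 gives neither, and it gives no reason why a figure from the cited guidance carries over to this mask in home use.

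What is at stake is how a reader interprets a problem that was not seen. Taken at face value, 9.6 suggests that little has been missed. For an uncommon problem, absence among 30 users is much weaker evidence than that.

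**Working it through.** **Inputs from the documents.** Section 9.6 gives n = 30 users, a ceiling of 45 recruited, and shares of 97% (minimum) and 99% (average). Going from 45 to 30 allows a loss of 1 − 30/45 = 33.3%.

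**Inputs not in the visible text.** These are p, the chance that a given user meets a given problem during home use, and d, the chance that the problem is detected when it occurs. The values of p below are assumptions, shown as a range. I take users as independent and d = 1 unless stated.

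**Step 1: the plan's own figures.** The 97% and 99% cannot be reproduced, because no p is given. The formula can only be inverted to show what p each figure would correspond to if it were the chance of seeing one given problem:

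- P(seen at least once) = 1 − (1 − p)^n, so p = 1 − (1 − P)^(1/n).
- For 97%: 1 − 0.03^(1/30) = 11.0%, and 1 − 0.03^(1/45) = 7.5%.
- For 99%: 1 − 0.01^(1/30) = 14.2%, and 1 − 0.01^(1/45) = 9.7%.

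**Step 2: the chance of seeing one given problem.** For example, at p = 5% and n = 30, 1 − 0.95^30 = 78.5%.

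| Share of users affected (assumed) | 30 users | 45 users |
|---|---|---|
| 1% | 26.0% | 36.4% |
| 5% | 78.5% | 90.1% |
| 10% | 95.8% | 99.1% |
| 11% | 97.0% | 99.5% |
| 15% | 99.2% | 99.9% |

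**Step 3: relation to 9.6's quantity.** Section 9.6 speaks of the share of all problems found, which is not the same as the chance of seeing one problem. The two are linked: the expected share is the average of the individual chances over all the problems that exist. If every problem affected at least 11.0% of users, the expected share with 30 users would be at least 97%. The more of the problems that are rarer than this, the lower the expected share. Without the frequencies it cannot be computed for this mask.

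**Step 4: what a problem not seen allows one to say.** If none of n users shows the problem, the one-sided 95% upper bound on p solves (1 − p)^n = 0.05:

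- n = 30: 1 − 0.05^(1/30) = 9.5%.
- n = 45: 1 − 0.05^(1/45) = 6.4%.

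**Step 5: imperfect detection.** Replacing p by d × p divides each threshold by d. With d = 0.7 (assumed), the 97% points become 0.1103/0.7 = 15.8% for 30 users and 0.0750/0.7 = 10.7% for 45. The upper bounds become 0.0950/0.7 = 13.6% and 0.0644/0.7 = 9.2%.

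**The case against.** The strongest reply is that the figures belong to the cited guidance. They may be empirical results for a defined set of problems, in which case the condition lies in the source and 9.6 merely fails to repeat it. This stands in part. A reader might infer from the table that 97% and 99% are wrong or misquoted. The documents do not support that, because the source is not available here and 9.6 supplies no frequency to test them against. What remains is that the protocol applies the figures to its own 30 users without the condition.

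A second reply is that this is a product-development study with no planned test, and that section 9.8 says statistical outcomes will not alter its conduct. That is correct, and it limits the weight. A reader might infer that 30 or 45 is too few. That does not follow, since nothing in the documents sets a detection target for rare problems.

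Third, the harm is hypothetical. No visible passage plans to report that 97% of problems were found. Section 11 permits wider use of the results, but it refers to clinical efficacy and not to the share of problems found, so it does not turn 9.6 into a planned claim.

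Fourth, 9.6 rests on a usability guidance, whereas 10.2 lists adverse events, which have their own recording rules in section 10. Nothing says that 9.6 was meant to size the detection of allergies or eyelid injury. This stands, and a bound for every item in 10.2 is therefore optional.

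Fifth, the analysis set in 9.10 includes anyone who attempted to sleep with the mask. Used as the denominator for a statement about the whole home-use period, it would count early dropouts as fully exposed and make the bound too low. This also stands and is met in the fix.

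Finally, parts of the protocol are not visible. Sections 6.3 and 6.4 are redacted, the contents list a section 9.7 on pass/fail criteria whose text does not appear, and the questionnaires are absent. A definition of a problem, or a rule for drawing conclusions, could be there. The point is therefore limited to the visible text.

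**Conclusion.** The point holds as a missing condition in the sample-size justification, at low severity. An unconditional minimum of 97% does not follow from 30 users. Under independence and certain detection, the chance of seeing one given problem runs from 26% at a frequency of 1%, through 79% at 5%, to 97% at about 11%. With 45 users it is 36% at 1% and 90% at 5%, and 97% is reached at about 7.5%. Imperfect detection lowers all of these chances. The frequencies are assumed, since the documents give none, and the chances concern one given problem and not the share of all problems.

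The conclusion concerns what may be said about problems that were not observed. Neither the number of participants nor the conduct of the study needs to change.

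**What to change.** Keep 30 evaluable and up to 45 recruited. In 9.6, replace the unconditional sentence with wording such as:

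*Assuming independent users, and detection whenever a problem occurs, 30 users give about a 97% chance of seeing a given problem that affects 11% of users, 79% at 5% and 26% at 1%. With 45 users the chance is 97% at about 7.5%, 90% at 5% and 36% at 1%. Imperfect detection lowers these chances.*

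Do not conclude from the study that 97% of problems were found. Where the report says that a problem was not observed, give the one-sided 95% upper bound on its frequency, 1 − 0.05^(1/n), with n the number actually observed (9.5% for 30, 6.4% for 45). If the statement is about the home-use period, take n as the number who completed that period, not everyone included under 9.10. Note that the bound assumes detection whenever the problem occurs.

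One clerical correction: the citation mark in 9.6 is 6, which in section 13 is a study of interface type. The guidance is reference 7.

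The cost is a rewritten passage in 9.6, a corrected reference number and a bound beside each such statement in the report. No participants are added and conduct is unchanged. The only drawback is that the stated figures look less favourable.
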